9.2.2 REGULATORY REPORTING

Suspected (considered related to the study drug) and unexpected (not previously described in the reference safety document) serious adverse reactions (SUSARs) will be reported in an expedited manner by GTx, Inc. to applicable Regulatory Authorities, EudraVigilance, IECs and IRBs, and Investigators in compliance with FDA regulations 21 CFR 312.32, ICH guidelines, the European Clinical Trials Directive 2001/20/EC, the European Commission's "Detailed guidance on the collection, verification and presentation of adverse event/reaction reports arising from clinical trials on medicinal products for human use" (CT-3, June 2011), and other applicable local regulations and guidelines, as required. The timelines stipulated by applicable national regulations and guidelines shall be adhered to, typically death and life-threatening SUSARs shall be reported within 7 days and all other SUSARs shall be reported within 15 days.

Additionally, events may occur during a clinical trial which do not fall within the definition of a SUSAR and thus are not subject to the reporting requirements for SUSARs, even though they may be relevant in terms of subject safety. Examples are new events

related to the conduct of a trial or the development of an IMP likely to affect the safety of subjects such as:

- A SAE which could be associated with the trial procedures and which could modify the conduct of the trial
- A significant hazard to the subject population such as lack of efficacy of an IMP used for the treatment of a life-threatening disease
- A major safety finding from a newly completed animal study (such as carcinogenicity)

These events/observations are not to be reported as SUSARs, but they might require other action, such as urgent safety measures and their notification, substantial amendments, or early termination of the trial, and shall be reported in accordance with applicable local regulations and guidelines.

All serious events designated as expected and/or “not related” to study drug(s), will be reported to the applicable Regulatory Authorities and IECs/IRBs at least annually in a summary format”.

9.3 TYPE AND DURATION OF FOLLOW-UP OF SUBJECTS AFTER ADVERSE EVENTS

AEs will be collected up until 28 days after the last dose of study treatment, and will continue to be followed up until one of the following occurs:

Resolved or improved to baseline

Death

Investigator confirms that no further improvement can be expected

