Statistical Considerations:	
This is a proof of concept feasibility study, so no power calculation is needed. Therefore, up to 35 subjects meeting inclusion/exclusion criteria will be recruited until 30 subjects have completed treatment. Descriptive statistics will be performed to explore changes in primary and secondary outcomes measures between baseline and end of treatment. The primary efficacy measure will be a reduction in the number of stress incontinence episodes/day. Secondary efficacy measures will include reduction in number of voids per day, volume of voids, 24 hour pad weight, responses to validated questionnaires, changes in UPP measures, changes in sexual function, and changes in pelvic floor muscles as measured by MRI.
 
Safety will be determined by the number and type of adverse events reported during treatment. Various imputation methods may be explored.

Study Intervention/Treatment:	
Participation in this study includes 5 in person study visits and two telephone and/or mailed questionnaire visits. Additional in person and/or telephone visits may be added as needed.
 
Study subjects will receive 3 mg of GTx-024 orally daily.

Table 1. Schedule of Measures.

	Screening Visit Days -21-0	Additional Screening Days -21-0	Visit 1. Baseline³ Week 0	Visit 2. Week 1 ± 3 days	Visit 3. Week 4 ± 3 days	Visit 4. Week 8 ± 3 days	Visit 5. Week 12 ± 3 days	Visit 6. Week 16 ± 7 days
	Clinic Visit	Clinic Visit	Clinic Visit	Phone Call	Clinic Visit	Clinic Visit	Clinic Visit	Phone Call and Mail
Consent	x							
Inclusion/Exclusion	x		x					
History			x					
Interview/Vital Signs	x		x		x	x	x	
Height/Weight	x				x	x	x	
24 hour Pad Weight	Instruct		x		x	x	x	
3 day Voiding Diary	Instruct		x		x	x	x	
Serum AST, ALT, Total Bilirubin	x				x	x	x	
Serum FSH ¹ ,	x							
CBC			x				x	
UA Dipstick (with culture as needed)	x		x				x	
Lipid Panel			x				x	
Testosterone Levels			x				x	
SHBG			x				x	
UPP			x				x	
Pelvic MRI		x					x	
Bladder Stress Test	x						x	
Mammogram ²		x						
Begin Daily ⁴ Treatment			x					
End Treatment							x	
Concomitant Meds	x		x	x	x	x	x	x
Adverse Events			x	x	x	x	x	x
HIV, Hep A, B, C Testing	x							
UDI-6; IIQ			x		x	x	x	x
PGI-S			x		x	x	x	x
MESA Questionnaire	x				x	x	x	x
PGI-I					x	x	x	x
FSFI Questionnaire			x		x	x	x	x
Bladder Scan PVR			x		x	x	x	
Ciprofloxacin 500 mg po (or equivalent)			x				x	
Focused Physical Exam			x				x	

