4. METHODOLOGY

4.1 STUDY DESIGN

This is a single site, proof of concept feasibility study to describe the effect of GTx-024 3 mg in postmenopausal female subjects with SUI. Postmenopausal will be defined as clinically confirmed female subjects who have undergone the onset of spontaneous, medical or surgical menopause prior to the start of this study. Durability of treatment will also be explored by evaluating validated measures at 4 weeks after last dose. Up to 35 subjects will be enrolled in this study.

Institutional Review Board (IRB) approval from Beaumont's Human Investigations Committee will be obtained prior to beginning any study activity. Once IRB approval is obtained, potential participants will be identified from existing medical records, or physician or other referrals.

Potential subjects may be prescreened by telephone prior to the first in person study visit (initial screening visit). At the first in person study visit, subjects will be seen in the Urology Clinical Research space and informed consent will be obtained prior to any study activity. At Study Visit, 2, inclusion/exclusion criteria will be verified, study data will be collected, and consented participants may begin treatment.

Enrolled subjects will agree to maintain on a stable dose of any medication known to affect lower urinary tract function, including but not limited to anticholinergics, tricyclic antidepressants, or alpha-adrenergic blockers, throughout the treatment and follow-up period. Subjects enrolled in the study will agree to not start any new treatment (medication or otherwise) that is known to affect lower urinary tract function throughout the treatment and follow up periods. Subjects will also agree to refrain from performing any Kegal exercises and maintain current dietary habits throughout the treatment and follow up periods.

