concomitant meds and adverse events, including any vaginal bleeding, discharge, infections and/or spotting, will be assessed and recorded. Subjects will also be instructed to complete a 24 hour pad weight and 3 day voiding diary in the week preceding their next study visit. A 30 day supply of study drug will be dispensed with administration instructions.

Study Visit 4: Week 8, Clinic Visit

Approximately 8 weeks after beginning treatment, subjects will return to the clinical research office for an in person visit. An interview and vital signs will be conducted. Height and weight and PVR will be measured. Pad weights will be measured, and the 3 day voiding diary will be collected and reviewed. Blood will also be drawn to measure serum AST, ALT, and total bilirubin. Questionnaires will also be completed and concomitant meds and adverse events including any vaginal bleeding, discharge, infections and/or spotting, will be assessed and recorded. Subjects will also be instructed to complete a 24 hour pad weight and 3 day voiding diary in the week preceding their next study visit. A 30 day supply of study drug will be dispensed with administration instructions.

Study Visit 5: Week 12, Clinic Visit

Approximately 12 weeks after beginning treatment, subjects will return to the clinical research office for an in person visit. An interview with vital signs will be conducted. A focused physical exam will be done. Gynecological pelvic exam will only be done at this visit if clinically indicated. Urine dipstick will be done and PVR will be measured. Height and weight will be measured. 24 hour pad weights and 3 day voiding diaries will be collected/reviewed. Blood will also be drawn to measure laboratory values as outlined in Table 1. UPP, Bladder Stress Test, and MRI will be performed at end of treatment, questionnaires will be administered, and concomitant medications/adverse events will be assessed and recorded. All study medication will be collected and accounted for.

Study Visit 6: Week 16, Telephone/mailed questionnaire visit

Approximately 4 weeks after study drug treatment has ended, subjects will be contacted by phone to assess for concomitant meds and adverse events. Subjects will also be instructed to complete and return mailed questionnaires.

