7.2 EARLY TERMINATION

Subjects may withdraw from the study voluntarily. In addition, if the PI determines that continued participation might present a safety risk for the subject then the PI may withdraw the subject from the study. Those subjects who receive study drug will be followed for 28 days after stopping study participation. Every effort will be made to obtain all end of treatment measures as outlined in (Table 1.Visit 6) in the event that a subject withdraws, or is withdrawn, from the study before completing treatment.

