9. ASSESSMENT OF SAFETY

9.1 METHODS AND TIMING FOR ASSESSING, RECORDING, AND ANALYZING SAFETY PARAMETERS

9.1.1 ADVERSE EVENTS

ICH E6 defines an AE as any untoward medical occurrence in a subject or clinical investigation subject administered a pharmaceutical product regardless of its causal relationship to the study treatment. An AE can therefore be any unfavorable and unintended sign (including an abnormal laboratory finding), symptom, or disease temporally associated with the use of a medicinal (investigational) product, whether or not considered related to the medicinal (investigational) product.

The occurrence of an AE may come to the attention of study personnel during study visits and interviews of a study subject presenting for medical care, or upon review by a study monitor.

The period of observation for which AEs are to be collected begins after the subject has signed the ICF, throughout the study intervention period, and for 28 days post treatment.

All AEs, whether reported by the subject or noted by study personnel, will be recorded in the subject's medical record and captured on the appropriate CRF.

Information to be collected includes event description, time of onset, Investigator's assessment of severity, Investigator's assessment of relationship to study drug, and time of resolution/stabilization of the event. All AEs occurring while on study must be documented appropriately regardless of relationship to study drug. All AEs will be followed to adequate resolution as per [Section 9.3 TYPE AND DURATION OF FOLLOW-UP OF SUBJECTS AFTER ADVERSE EVENTS](#).

Any medical condition that is present at the time that the subject is screened will be considered as baseline and not reported as an AE. However, if the condition deteriorates at any time during the study, it will be recorded as an AE. All AEs must be graded for intensity and relationship to study drug.

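### The Visit 6 window lets the last scheduled adverse event contact for completers fall on day 21 after last dose, a week before the 28-day collection period ends

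*Combined protocol and SAP*

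**What the plan says.** The collection period is stated consistently. Section 9.3 says "AEs will be collected up until 28 days after the last dose of study treatment". Section 9.1.1 starts the period at consent and continues it "throughout the study intervention period, and for 28 days post treatment". Section 9.2.1 requires reporting of SAEs over the same 28 days after the last administration.

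Treatment ends at Visit 5 (Week 12 ± 3 days in Table 1), when all study medication is collected. One contact is scheduled after that, which Table 1 shows as "Visit 6. Week 16 ± 7 days", by telephone and mail. Section 7.1 describes it in words: "Approximately 4 weeks after study drug treatment has ended, subjects will be contacted by phone to assess for concomitant meds and adverse events". Section 4.1 gives the same timing for the durability assessment: "evaluating validated measures at 4 weeks after last dose".

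Two other provisions bear on the point. The Protocol Summary allows extra contacts: "Additional in person and/or telephone visits may be added as needed". Section 7.2, on early termination, provides: "Those subjects who receive study drug will be followed for 28 days after stopping study participation". Section 5.4.2 has a comparable provision for subjects already treated if the study is stopped.

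**The concern.** The length of the AE/SAE period and the window of the visit that serves it do not match. The nominal visit falls on the last day of the period, but a symmetric window around that day places almost half of the permitted dates before the period ends. A site can follow Table 1 exactly, make the call early, and then have no scheduled reason to ask the subject anything more.

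After such a call, an event before day 28 comes to light only if the subject volunteers it or by one of the other routes in Section 9.1.1, such as the subject "presenting for medical care, or upon review by a study monitor". Neither of those routes asks every subject. The 24-hour SAE reporting rule in Section 9.2.1 runs from when the investigator learns of the event, so it gives no protection against an event that nobody asked about.

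What is at stake is how complete post-treatment AE and SAE capture is in completers. Early withdrawals are outside the point, because Section 7.2 already sets 28 days of follow-up for them.

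**Working it through.** **Inputs**
- AE/SAE collection: to day 28 after last dose (Sections 9.1.1, 9.2.1, 9.3).
- Visit 5: Week 12 ± 3 days, so study days 81 to 87, nominal 84 (Table 1).
- Visit 6: Week 16 ± 7 days, so study days 105 to 119, nominal 112 (Table 1).
- Completers: 30 (Section 10).
- Assumption: the last dose is taken on the day of Visit 5, where Table 1 marks the end of treatment.

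**Nominal timing.** 112 − 84 = 28 days. This reproduces the protocol's own 28-day period, so there is no gap on the nominal dates.

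**Window counted from the last dose.** 28 ± 7 gives days 21 to 35, which is 15 permitted days. Days 21 to 27, 7 of the 15, come before day 28. The largest uncovered stretch is 28 − 21 = 7 days.

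**Other readings of the anchor**
- Last dose on the day before Visit 5, with the call timed from Visit 5: the earliest call is day 22, and the largest gap is 6 days.
- Both windows counted from baseline: the earliest call is (112 − 7) − (84 + 3) = day 18, a gap of 10 days. The latest is (112 + 7) − (84 − 3) = day 38. Of the 7 × 15 = 105 permitted pairs of visit dates, 49 put the call before day 28.

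**Person-days for 30 completers.** The total post-treatment period is 30 × 28 = 840.

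| All calls made on | Person-days after last scheduled contact | Share of 840 |
|---|---|---|
| Day 28 or later | 0 | 0% |
| Day 25 | 30 × 3 = 90 | 10.7% |
| Day 21 | 30 × 7 = 210 | 25% |

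The documents do not say how call dates will be spread, so the table gives bounds and one intermediate case.

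**Proposed window.** With 0/+7 days from last dose, the permitted days are 28 to 35, and 0 of 8 come before day 28. The anchor matters: a Week 16 window of −0/+7 counted from baseline would still allow 112 − 87 = day 25.

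**The case against.** The strongest reply is that the protocol already handles this. The 28-day duty stands apart from Visit 6, so a site that calls on day 21 still owes collection to day 28. The Protocol Summary lets it add a call, and Section 7.1 tells it to aim for about 4 weeks. On that view an early call is exactly when an extra contact is needed, and what is missing is only a dated backup.

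That does not close the gap. Permission to add a contact obliges nobody to make one, and the approximate wording in Section 7.1 is given its numeric limits by Table 1, which a day-21 call satisfies.

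The second line is that little is lost, and much of this stands:
- Section 10 summarises AEs reported during treatment, so no planned table changes.
- The drug effects singled out in Section 2.2.1 are asymptomatic ALT rises and HDL reductions. Visit 6 has no blood draw, so a later call would detect neither.
- Events already found by an early call must still be followed under Section 9.3.
- The 25% figure needs every call on the earliest permitted day, and person-days without a contact are not missed events.

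These points limit the importance of the finding. They do not remove the mismatch, because post-treatment collection and SAE reporting are obligations of the protocol in their own right.

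The third line is that an amendment is heavier than needed. This is partly right, and the first step of the fix needs none.

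**Conclusion.** The concern holds. Under the schedule as written, the last planned AE inquiry for a completer can take place on day 21 after last dose, up to 7 days before the AE/SAE period closes, with no later contact required. The gap is 6 days if the last dose is the day before Visit 5 and the call is timed from Visit 5, and 10 days only if both visit windows are counted from baseline. On nominal dates it is zero.

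For 30 completers the bounds are 0 to 210 of 840 person-days. No expected number of missed events can be derived from the documents. The consequence is a small possible loss of post-treatment AE and SAE information. Efficacy results and the planned on-treatment safety summary are unaffected. The change is worth making because it costs so little.

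**What to change.** Redefine Visit 6 in Table 1 as 28 days after the actual last dose, with a window of 0 to +7 days (days 28 to 35), and align Section 7.1 with it. No permitted call date then falls before the end of the AE/SAE period.

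Until that is approved, the site can be told to call on or after day 28 following Visit 5. That date is already in window on either reading: with Visit 5 on study days 81 to 87, it is study day 109 to 115, inside 105 to 119. Anyone reached earlier can be given a second short call under the existing provision for additional contacts.

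Cost: a change of window and anchor, with no added visit. It needs IRB approval as an amendment (Section 12.8), so it is cheapest combined with another one. Counted from end of treatment, the latest date stays at day 35. Longest participation is 21 + 87 + 35 = 143 days, within the stated 5 months. The permitted days fall from 15 to 8, and for some subjects the Visit 6 durability questionnaires come a few days later, though this fits the timing set in Section 4.1.

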9.4 HALTING RULES

If in the opinion of the Investigator, the participation in the study is or is becoming detrimental to the well-being of a particular subject, this issue should be discussed with the Medical Monitor for this study and the subject’s participation in the study may be discontinued.

Discontinuation of treatment should be considered if:

ALT or AST > 8 × ULN

ALT or AST > 5 × ULN for more than 2 weeks

ALT or AST > 3 × ULN and ((total bilirubin > 2 × ULN or INR > 1.5)

ALT or AST > 3 × ULN with the appearance of fatigue, nausea, vomiting, right upper quadrant pain or tenderness, fever, rash, and/or eosinophilia (> 5%)

All subjects discontinued from the study should be followed until abnormal values return to normal.

ALL DISCONTINUATIONS SHOULD BE DISCUSSED WITH THE MEDICAL MONITOR PRIOR TO DISCONTINUATION.

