2.2 RISKS ANALYSIS AND RISK ASSESSMENT

2.2.1 POTENTIAL ANTICIPATED ADVERSE EVENTS

An adverse event is any clinical event that impacts, or that has the potential to impact, the health or safety of a Clinical Study subject caused by or associated with the study device and/or testing. Assessment for potential adverse events will be ongoing throughout this trial.

The benefits of treatment may include improvement in the frequency, or severity of urine loss, and improvement in quality of life. Decreases in serum triglycerides, cholesterol, and body fat, and improvements in insulin resistance, lean body mass and physical endurance are also possible benefits.

Adverse event tables and serious adverse events discussed below and are presented separately by adverse events reported among healthy volunteers on a single trial of 86 days of GTx-024 3 mg versus placebo and those enrolled on cancer trials of at least 86 days exposure to GTx-024 3 mg or placebo.

Adverse events reported among > 5% of GTx-024 3mg treated healthy subjects
Percentage of subjects reporting a given adverse event at least once

Primary System Organ Class	Preferred Term	GTx-024 N=24	Placebo N=24
Gastrointestinal disorders	Diarrhea	8.3	12.5
	Dyspepsia	8.3	8.3
	Vomiting	8.3	0.0
General disorders and administration site conditions	Vessel puncture site bruise	12.5	4.2
	Fatigue	8.3	8.3
	Malaise	8.3	0.0
Infections and infestations	Herpes simplex	8.3	0.0
Injury, poisoning and procedural complications	Contusion	8.3	4.2
Investigations	Alanine aminotransferase increased	20.8	0.0
Musculoskeletal and connective tissue disorders	Back pain	12.5	16.7

Primary System Organ Class	Preferred Term	GTx-024 N=24	Placebo N=24
Nervous system disorders	Headache	20.8	20.8
	Dizziness	12.5	4.2
Respiratory, thoracic and mediastinal disorders	Pharyngolaryngeal pain	12.5	12.5

No serious adverse events (SAEs) were reported on this trial.

These side effects are based on information obtained from a clinical study (G200501) administering GTx- 024 3 mg for 86 days in healthy subjects– elderly males and postmenopausal females. Studies suggest that side effects associated with the study drug resolve after GTx-024 is stopped.

**Adverse events reported among > 5% of GTx-024 3 mg treated cancer subjects
Percentage of subjects reporting a given adverse event at least once**

Primary System Organ Class	Preferred Term	GTx-024 N=432	Placebo N=378
Blood and lymphatic system disorders	Anemia	34.7	34.7
	Neutropenia	18.3	23.3

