	Thrombocytopenia	10.4	10.8
	Leukopenia	8.3	9.0
Gastrointestinal disorders	Nausea	34.7	34.9
	Vomiting	20.1	21.2
	Constipation	12.3	10.1
	Diarrhea	11.6	12.7
General disorders and administration site conditions	Abdominal pain	5.1	3.7
	Fatigue	15.7	16.7
	Asthenia	15.3	13.5
	Disease progression	11.8	16.7
Infections and infestations	Pyrexia	10.2	9.8
	Pneumonia	5.6	7.1
Investigations	Blood creatinine increased	8.1	5.0

Primary System Organ Class	Preferred Term	GTx-024 N=432	Placebo N=378
	Weight decreased	6.0	4.8
Metabolism and nutrition disorders	Decreased appetite	10.6	14.8
Musculoskeletal and connective tissue disorders	Arthralgia	8.1	7.9
	Pain in extremity	5.6	4.2
Nervous system disorders	Headache	7.4	6.1
	Peripheral sensory neuropathy	5.8	3.4
	Dizziness	5.6	6.3
Respiratory, thoracic and mediastinal disorders	Dyspnoea	12.3	7.4
	Cough	9.5	9.3
Skin and subcutaneous tissue disorders	Alopecia	17.8	18.5

Serious adverse events (SAEs) reported among > 2% of GTx-024 3 mg treated cancer subjects

Percentage of subjects reporting a given serious adverse event at least once

Primary System Organ Class	Preferred Term	GTx-024 N=432	Placebo N=378
Blood and lymphatic system disorders	Anemia	4.2	3.7
	Neutropenia	3.2	3.7
	Febrile neutropenia	2.3	1.6
Blood and lymphatic system disorders	Thrombocytopenia	2.3	1.6
General disorders and administration site conditions	Disease progression	7.9	11.9
Infections and infestations	Pneumonia	3.5	3.2
Neoplasms benign, malignant and unspecified (incl cysts and	Malignant neoplasm progression	2.8	2.1

An AE that appears related to GTx-024 in clinical trials has been a dose-dependent, transient, asymptomatic increase in ALT. However, these increases were modest at doses up to 10 mg per day. Most of the subjects studied to date had ALT levels that

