remained within normal limits. One subject was discontinued for an ALT > 3 times the ULN. The ALT levels returned to normal with continued exposure to GTx-024 in most cases and, further, in instances when dosing was not continued, levels returned to normal. No significant increases in total bilirubin, gamma glutamyl transferase, alkaline phosphatase, or lactate dehydrogenase have been observed in subjects with elevated ALT levels. Consistent with the effects of other orally administered anabolic agents, GTx-024 causes a dose dependent reduction in high-density lipoprotein (HDL), the clinical significance of which is unknown at this time. The proposed mechanism for reduction in HDL is due to stimulation of reverse cholesterol transport and increased HDL catabolism by hepatic lipase. Reductions in HDL are temporary and typically return to baseline 12 months after treatment initiation.

The effect of GTx-024 on a fetus has not been evaluated; therefore, the subjects in the current investigation will be post-menopausal.

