2.2.3 METHODS TO MINIMIZE RISK

Subjects will be monitored at each visit for changes since last visit and adverse effects of treatment. Since elevations in ALT are possible, serum liver function tests will be monitored during treatment. (Refer to Section 9.4 Halting Rules)

Subjects will receive a prophylactic antibiotic at visits where catheterization/UPP occur to decrease risk of urinary tract infection (UTI). Any infection will be appropriately treated.

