4.2 MEDICAL MONITORING

A Medical Monitor will be responsible for monitoring the safety and data of this trial. The data that will be monitored include adverse events related to the study drug and procedures.

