9.1.2 INTENSITY OF EVENT

All AEs will be assessed by the Investigator according to NCI-CTCAE, Version 4.0. For any AE that is not specifically covered in NCI-CTCAE, Version 4.0, the criteria from

Table 1 should be used:

Table 1: Description of Grades According to the CTCAE	
Grade	Description
0	No AE or within normal limits
1	Mild; asymptomatic or mild symptoms; clinical or diagnostic observations only; intervention not indicated
2	Moderate; minimal, local, or non-invasive intervention indicated; limiting age-appropriate instrumental activities of daily living
3	Severe or medically significant but not immediately life-threatening; hospitalization or prolongation of hospitalization indicated; disabling; limiting self-care activities of daily living
4	Life threatening consequences; urgent intervention indicated
5	Death related to AE

If the intensity changes within a day, the maximum intensity should be recorded. If the intensity changes over a longer period of time, the changes should be recorded as separate events (having separate onset and stop dates for each change in intensity). Changes in the intensity of an AE will be documented to allow an assessment of the duration of the event at each level of intensity to be performed. AEs characterized as intermittent require documentation of onset and duration of each episode.

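### Section 9.4's 2-week persistence criterion for ALT/AST has no required repeat test, and the scheduled on-treatment liver tests are 22 to 34 days apart

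*Combined protocol and SAP*

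**What the plan says.** Section 9.4 lists four liver criteria, each a ground for considering (not mandating) discontinuation. One depends on duration: "ALT or AST > 5 × ULN for more than 2 weeks". The section sets no repeat test for a subject still on drug. Its only follow-up duty, until values are normal, applies to subjects already discontinued.

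Table 1 schedules AST, ALT and total bilirubin at Screening and at Weeks 4, 8 and 12, with ± 3 days on the on-treatment visits. Section 7.1 agrees. The Week 1 and Week 16 contacts are remote and include no blood draw. Treatment ends at Week 12.

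Section 2.2.3 presents liver monitoring as the safeguard and refers to 9.4: "Since elevations in ALT are possible, serum liver function tests will be monitored during treatment". Section 2.2.1 explains why: "An AE that appears related to GTx-024 in clinical trials has been a dose-dependent, transient, asymptomatic increase in ALT".

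Several general provisions bear on an earlier retest:
- The Protocol Summary allows additional visits when needed.
- Section 9.1.1 counts as an AE "any unfavorable and unintended sign (including an abnormal laboratory finding), symptom, or disease".
- Section 9.1.2 says that changes in AE intensity "will be documented to allow an assessment of the duration of the event at each level of intensity".
- Section 9.3 has AEs followed to resolution.
- Section 4.2 gives the Medical Monitor a role: "The data that will be monitored include adverse events related to the study drug and procedures".

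**The concern.** A single reading cannot show that a value has lasted more than two weeks, and the next scheduled reading comes well after two weeks. The stated rule and the stated schedule therefore do not fit each other, and the mismatch falls on the one laboratory signal that the protocol attributes to the drug.

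The other criteria may not fill the gap. Section 2.2.1 describes the ALT rise as asymptomatic and reports no significant bilirubin increase in subjects with raised ALT. A rise of that kind would not meet the bilirubin or symptom criteria. Between 5 and 8 × ULN, the duration criterion may be the only one that applies. What is at stake is the timing of a safety decision, measured in days of further dosing. The efficacy analyses are not affected.

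**Working it through.** The plan gives no figure for this delay, so there is none to reproduce. The check is visit-window arithmetic plus a reading of which criterion covers which case.

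**Inputs**
- Persistence threshold: more than 14 days (Section 9.4).
- On-treatment liver tests: Weeks 4, 8 and 12, each ± 3 days (Table 1). Each visit is timed from the start of treatment (Section 7.1), so neighbouring windows vary independently.
- Entry requires normal AST and ALT (Section 5.1), so the first scheduled reading that could exceed 5 × ULN is at Week 4.
- Dose: one capsule a day (Section 6.5).
- Supply: 30 days at Weeks 4 and 8 (Section 7.1); bottles hold 35 days of drug (Section 6.3).
- Assumption: the result is known on the day of the draw.

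**Step 1, visit days.** Week 4: 28 ± 3 = days 25 to 31. Week 8: 56 ± 3 = days 53 to 59. Week 12: 84 ± 3 = days 81 to 87.

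**Step 2, gap between tests.**
- Week 4 to 8: shortest 53 − 31 = 22 days, longest 59 − 25 = 34 days.
- Week 8 to 12: shortest 81 − 59 = 22 days, longest 87 − 53 = 34 days.
- Nominal gap: 28 days in both cases.

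**Step 3, delay from the first scheduled reading above 5 × ULN.**
- Past the 14-day mark: 22 − 14 = 8 to 34 − 14 = 20 days (nominal 14).
- Past day 15, the first day that is more than two weeks: 22 − 15 = 7 to 34 − 15 = 19 days.

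**Step 4, doses taken in that delay.** At the shortest gap, 8. At the longest gap the answer depends on supply. If the 30-day supply is literal, drug runs out at day 30 and the maximum is 30 − 14 = 16. If a full 35-day bottle is given, the maximum is 34 − 14 = 20. Section 7.1 calls the 35-count bottle at Visit 1 a one-month supply, so either reading is possible.

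**Step 5, what the rule can do on the schedule alone.**

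| First value above 5 × ULN | Persistence read at | Can it shorten dosing? |
|---|---|---|
| Week 4 | Week 8 | Yes, 8 to 20 days after the 14-day mark |
| Week 8 | Week 12 | No, dosing ends at that visit |
| Week 12 | No later scheduled test | No, dosing has ended |

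**Step 6, which subjects are affected.** Above 8 × ULN, one reading meets a criterion. Above 3 × ULN with bilirubin above 2 × ULN, or with the listed symptoms, one visit is also enough. What remains is ALT or AST of 5 to 8 × ULN with neither.

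**Step 7, how often.** The documents give no rate for that case. What they give on ALT is:
- "Alanine aminotransferase increased": 20.8% of 24 healthy elderly men and postmenopausal women on 3 mg, that is 0.208 × 24 = 5 subjects, against 0 of 24 on placebo.
- The table of AEs in more than 5% of 432 cancer subjects on 3 mg has no ALT row. Its Investigations entries are creatinine and weight.
- "One subject was discontinued for an ALT > 3 times the ULN", with no denominator.
- Section 2.2.1 calls the increases modest up to 10 mg a day, says most subjects' ALT stayed normal, and says raised values normalised during further dosing in most cases.

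None of these isolates 5 to 8 × ULN.

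**The case against.** The strongest reply is that the delay presupposes inaction. An investigator who sees a value above 5 × ULN would have to order nothing for three to five weeks. A rule framed in weeks implies a repeat test. Sections 9.1.2 and 9.3 use mandatory wording on AE duration and follow-up, and extra visits are allowed. This stands in part: early retesting is open to the investigator and likely in practice. But none of these provisions names a liver test or sets an interval, so none puts the criterion on its own 14-day clock.

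A reader might infer more than the documents support:
- *That no retest step exists anywhere.* Section 11 refers to standard operating procedures and Section 13.5 to a Manual of Procedures. Neither was supplied, and a step could sit there. The point is limited to the protocol text.
- *That about 7 of 35 subjects are at risk, by applying 20.8%.* That rate is for any ALT increase, in 24 subjects who included men. The far larger cancer sample on the same dose does not list the event above 5%. No projection to this trial is warranted.
- *That late reading means doses wrongly given.* The rule is advisory, and ALT mostly normalised on continued drug.
- *That the other liver criteria also fail.* INR appears only in 9.4, and the CBC is not drawn at Week 4 or 8. Each feeds one alternative within a criterion that otherwise works from scheduled bilirubin or from symptoms.

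**Conclusion.** The point holds as a mismatch between a rule and its schedule, and it is a cheap improvement rather than a serious flaw. The protocol text requires no repeat test for a 14-day criterion and spaces its scheduled tests 22 to 34 days apart. If nobody retests early, persistence is read 8 to 20 days after the 14-day mark (7 to 19 counted from day 15). That means 8 to about 16 late doses if the 30-day supply is literal, or up to 20 with the 35-day bottles. A first such value at Week 8 is read only when dosing ends.

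These figures rest on two conditions: that only scheduled tests are used, and that the count starts at the first scheduled reading above 5 × ULN. The affected case is narrow, its frequency is unknown, and the available evidence on ALT is mostly reassuring. The reason to act is that this is the drug's recognised signal and the correction costs very little.

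**What to change.** Add one sentence to Section 9.4 and repeat it as a Table 1 footnote: *Any on-treatment ALT or AST > 5 × ULN is repeated with total bilirubin within 1 week and, if still > 5 × ULN and dosing continues, again just after day 14 from the first such value.*

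Persistence would then be read at about day 15 rather than day 22 to 34, which removes 22 − 15 = 7 to 34 − 15 = 19 days. The rule could also act on a first raised value at Week 8.

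The cost is one extra blood draw if the first repeat is no longer above 5 × ULN, and two if it is and dosing continues, possibly with added visits, which the protocol already allows. Sample size, endpoints and analyses are unchanged. If the Manual of Procedures already holds such a step, a cross-reference in 9.4 is enough. A lower trigger at 3 × ULN with weekly testing, or adding INR and a CBC to the repeat, is optional and not needed to correct this point.
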